12. STATISTICAL METHODS

12.1 Study Design

This is an open label, single agent, multicenter, phase II study with 2 cohorts evaluating the efficacy of brentuximab vedotin in “CD30 positive” and “CD30 negative/unknown” relapsed/refractory NSGCT who are otherwise considered non-curable. Both cohorts will be treated similarly and in parallel but analyzed separately.

12.2 Endpoints

12.2.1 Definition of Primary Endpoint

Objective response rate is the proportion of patients who achieve either a partial or complete response

Complete response is defined as disappearance of all target lesions and normalization of serum tumor markers (AFP and beta-hCG) for at least 4 weeks. Any pathological lymph nodes (whether target or non-target) must have reduction in short axis to <10 mm.

Complete Response must be confirmed four or more weeks after initial CR is observed. In patients whose only evidence of disease is elevated serum tumor markers (AFP or beta-hCG), then values must fall below the upper limit of normal for the assay employed and remain at that level for at least 4 weeks.

Partial response is defined as at least a 30% decrease in the sum of the diameters of target lesions, taking as reference the baseline sum diameters. This should be present on at least 2 measurements 1 month apart. The serum tumor markers (AFP and beta-hCG) should be stable or decreasing. Partial Response must be confirmed four or more weeks after initial PR is observed.

In patients whose only evidence of disease is elevated serum tumor markers (AFP or beta-hCG), then values must fall $\geq 90\%$ below baseline pretreatment levels for beta-hCG or 50% decrease below baseline pretreatment levels for AFP and persist for 6 weeks. If both tumor markers are elevated and one falls below 90% the other should fall at least below 50% of baseline pretreatment levels.

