	
 4. Patients with measurable disease according to RECIST v1.1, or with rising AFP or BHCG above the upper limit of normal on two consecutive determinations if no measurable radiologic disease. 5. Patients with brain metastases are allowed onto the study as long as patients have completed their treatment for brain metastasis, no longer require corticosteroids, and are asymptomatic. Subjects with neurological symptoms should undergo a head CT scan or brain MRI to exclude brain metastasis, at the discretion of the treating physician. 6. Patients with ECOG performance status of 0-2. 7. Adequate organ and marrow function as detailed in the protocol. 8. Patients who are willing and able to comply with the protocol and study procedures including willingness to undergo tumor biopsy for tumor cells before therapy to assess for CD30 status (unless archival tumor tissue from orchiectomy or other previous sample is not obtainable despite efforts to do so and a fresh tumor biopsy is not feasible). 
Main Exclusion Criteria:
 
 1. Patients with pure seminoma. 2. Patients with pure teratoma. 3. Chemotherapy within 2 weeks of initiating study treatment. 4. Major surgery within 3 weeks of starting study treatment. There is no minimum time requirement for minor procedures such as biopsy or vascular access placement. 5. Radiation within 2 weeks of starting study treatment. 6. \geq Grade 3 neuropathy at the time of enrollment. 7. Pregnancy or breast-feeding. 8. Previous treatment with any anti-CD30 directed therapy.

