visual central review was 25% in the responders vs. 25% in the nonresponders. Twenty-one percent of the responders had <10% CD30 expression. Two patients with DLBCL with ≤1% detectable CD30 expression by central pathologist review achieved CR. Although the precise mechanisms underlying this phenomenon remain unknown, some evidence indicates a 'bystander effect', whereby free MMAE is released from dying cells in concentrations sufficient to kill neighboring tumor cells(17) either directly or indirectly by altering the tumor microenvironment.(18)

Patients will be enrolled into two cohorts, one for CD30 positive patients and one for CD30 negative (or CD30 unknown). CD30 status may be unknown in the unlikely case of tumor-marker-only relapse or when a fresh tumor biopsy is not feasible, and archival tumor tissue is not obtainable despite efforts to do so. We would like to enroll such patients if they are otherwise eligible for the study and would include them in the CD30 negative cohort for analysis purposes, since statistically NSGCT are more likely to be CD30 negative. **The number of such patients with unknown CD30 status should not exceed 5 patients.**

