2.2 Endpoints

2.2.1 Primary Endpoint

Objective response (CR + PR) measured by RECIST Criteria v1.1 if there is measurable disease. In case of no measurable disease (marker-only patients), response can be assessed by either a reduction of BHCG by >90% (with no rise in AFP on two

consecutive measures) or a reduction of AFP by >50% (with no rise in BHCG on two consecutive measures).

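### Marker-only partial response with both markers elevated: the written rule mixes a remaining level with a size of fall and clashes with the single-marker rule beside it, so the same patient can be a responder or not

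*Combined protocol and SAP*

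**What the plan says.** The marker-only partial response (PR) rule appears in the same words in the synopsis (Statistical Considerations, item a), Section 9.5 and Section 12.2.1. It has two parts.

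- Single-marker rule: one limb says "values must fall $\geq 90\%$ below baseline pretreatment levels for beta-hCG". The other limb, for AFP, asks for a "50% decrease below baseline pretreatment levels for AFP and persist for 6 weeks". The two limbs are joined by *or*.
- Both-markers sentence: "If both tumor markers are elevated and one falls below 90% the other should fall at least below 50% of baseline pretreatment levels".

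Section 2.2.1 defines the same endpoint differently. Its beta-hCG limb begins "a reduction of BHCG by >90% (with no rise in AFP on two", meaning two successive readings. Its AFP limb mirrors this, with a fall of more than 50% and beta-hCG not rising; either limb is enough. Section 2.2.1 has no persistence period and asks only that the second marker not rise.

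Marker-only patients may enter "with rising AFP or BHCG above the upper limit of normal on two consecutive determinations if no measurable radiologic disease" (synopsis, inclusion criterion 4). Section 1.4 expects few of them: "CD30 status may be unknown in the unlikely case of tumor-marker-only relapse".

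Section 12.3 applies the response count to each cohort. No response in the first 10 patients closes the cohort, and 4 or more in 29 declares the drug active. The stated type I error is 0.047, the power 0.801 and the early termination probability under the null 0.599.

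**The concern.** In the single-marker rule, 90% is how far beta-hCG must fall. In the next sentence, read as written, 90% and 50% are levels relative to baseline that the markers must fall under. The 50% threshold is nearly the same either way. For 90% the two meanings are far apart: a fall of just over 10% or a fall of 90%.

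The sentence also does not say whether it replaces the *or* rule when both markers are raised, or whether the 6-week persistence applies to it. Two assessors could classify the same patient differently and both cite the protocol. With thresholds of 1 in 10 and 4 in 29, one patient can change a cohort's outcome. The trial is open label, so a choice of reading made after marker values are known would be hard to defend.

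**Working it through.** **Step 1. The plan's own figures.** Inputs from Section 12.3: 10 patients then 19 more, stop at 0 of 10, active at 4 or more of 29, null rate 0.05, alternative 0.20.

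- Early termination under the null = 0.95^10 = 0.5987.
- P(active) = Σ over k ≥ 1 of P(X1 = k) × P(X2 ≥ 4 − k), with X1 ~ Bin(10, p) and X2 ~ Bin(19, p).
- At p = 0.05: 0.3151 × 0.0665 + 0.0746 × 0.2453 + 0.0105 × 0.6226 + 0.0010 = 0.0468.
- At p = 0.20 the same sum gives 0.8011.

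All three stated figures reproduce. The problem is not in the design arithmetic.

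**Step 2. Classify falls under each rule.** Both markers are raised at baseline, falls are percentages of baseline, and any required persistence is assumed met.

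| Fall in beta-hCG / AFP | Single-marker *or* rule | Both-markers sentence, literal (>10% and >50%) | Both-markers sentence as 90% and 50% | Section 2.2.1 |
|---|---|---|---|---|
| 55% / 15% | no | **yes** | no | no |
| 92% / 20% | yes | yes | **no** | yes |
| 12% / 55% | yes | yes | **no** | yes |
| 92% / 55% | yes | yes | yes | yes |

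**Step 3. What each reading changes.**

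- Literal reading: an AFP fall of more than 50% already qualifies under the *or* rule, and so does a beta-hCG fall of 90% or more. The patients newly admitted are therefore only those with beta-hCG down by more than 50% but less than 90% and AFP down by more than 10% but less than 50% (first row).
- Reading as a 90% fall plus a 50% fall: this is stricter than the *or* rule and than Section 2.2.1. It removes patients whose response is in one marker only (second and third rows).

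The error thus runs in either direction, depending on the reading.

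**Step 4. Possible size for the type I error.** Two inputs are assumed because the documents give neither: m, the number of marker-only patients among 29, and q, the extra chance that each is counted as a responder. Those m patients respond with probability 0.05 + q and the others with 0.05. The result is averaged over how many of the m fall in stage 1, with weights C(10, j) × C(19, m − j) / C(29, m).

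| q (assumed) | m = 1 | m = 2 | m = 3 |
|---|---|---|---|
| 2% | 0.049 | 0.051 | 0.053 |
| 5% | 0.052 | 0.057 | 0.062 |
| 10% | 0.057 | 0.068 | 0.080 |
| 20% | 0.066 | 0.091 | 0.120 |

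Check for m = 1: one certain extra response gives 0.1627 if it falls in stage 1 and 0.1279 if in stage 2. The average is (10 × 0.1627 + 19 × 0.1279) / 29 = 0.1399. The probability is linear in that patient's response rate, so the slope is (0.1399 − 0.0468) / 0.95 = 0.098. At q = 20%, 0.0468 + 0.2 × 0.098 = 0.066, as tabulated.

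**The case against.** The best defence is that this is a drafting slip with a recoverable meaning. The preceding sentence and Section 2.2.1 both treat 90% as a reduction, and marker-only relapse is called unlikely. Section 3.1, criterion 4, also requires two consecutive rising values at least a week apart and no alternative cause of the elevation. This limits the number of patients affected and the scope for false elevations at entry. It does not settle the rule, because the probable meaning still contradicts the *or* rule and Section 2.2.1.

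Three stronger readings are tempting, and the documents do not support them.

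- *A 10% fall is enough for a response.* It is not: the other marker must still fall by more than 50%. Beta-hCG down 12% with AFP down 55% does not show the fault either, since the *or* rule already makes that patient a PR and Section 2.2.1 can too.
- *Complete response is easier than partial response, so the definitions are incoherent.* Marker-only complete response requires that "values must fall below the upper limit of normal for the assay employed and remain at that level for at least 4 weeks". From x times the upper limit of normal this takes a fall of 1 − 1/x, which is less than 50% for AFP below 2 times the limit and less than 90% for beta-hCG below 10 times. But sustained normalisation is a legitimate absolute criterion, and a small percentage fall from a low baseline is not in itself spurious. The 4-week versus 6-week difference largely disappears with markers drawn every 21 ± 3 days: one interval (18 to 24 days) cannot show 4 weeks, and two are nominally 42 days.
- *The type I error is inflated to about 0.12.* That figure needs three marker-only patients in a cohort and a 20% extra response chance in each. Both are assumptions. The extra chance could arise only in patients with both markers raised whose falls lie in the narrow band of Step 3.

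**Conclusion.** The point holds for the both-markers sentence and its conflict with the rules around it. The same patient can be a responder or a non-responder depending on the sentence applied, and the effect on the response count can go either way. For inflation alone, the assumed range of 1 to 3 patients and 2% to 20% takes the type I error from 0.047 to between 0.049 and 0.12; the lower end is negligible. These figures show sensitivity and do not estimate what will happen. The design's stated operating characteristics are correct, and the marker-only complete response criterion is not at fault. The correction is worth making because the wording defines the primary endpoint and can be settled before responses are assessed.

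**What to change.** Put one identical marker-only PR rule in the synopsis, Section 2.2.1, Section 9.5 and Section 12.2.1, with every threshold expressed as a percentage reduction from baseline. For patients with both markers elevated at baseline, state that:

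- PR requires a reduction of at least 90% in one marker and at least 50% in the other;
- this replaces the single-marker *or* rule for these patients;
- the 6-week persistence applies.

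Bringing Section 2.2.1 into line also removes its differences on persistence (none versus 6 weeks), on the second marker (no rise versus a required fall) and on the threshold (more than 90% versus at least 90%). Leave marker-only complete response unchanged.

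The cost is wording in four places and some lost responders: patients who respond in one marker only, such as beta-hCG down 92% with AFP down 20%, will no longer count. As an illustrative extreme, set the response probability to zero for two or three of the 29 patients and keep 0.20 for the rest. The Step 4 averaging then gives power of about 0.76 or 0.73 instead of 0.801. The real loss should be smaller, because only patients with both markers raised and a one-marker response are affected.

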12.2.2 Definition of Secondary Endpoints

Progression-free survival (PFS) is the time measured from the date of initiation of therapy until disease progression or death, whichever comes first. Patients alive and progression-free will be censored at their last disease assessment.

Overall survival (OS) is the time measured from the date of initiation of therapy until death, regardless of cause. Patients alive at the time of data analysis will be censored at their last date of contact.

12.3 Sample Size and Accrual

An optimal Simon two-stage design will be used for each cohort of patients to differentiate between the null hypothesis that the response rate P is $\leq 5\%$ ($P \leq 0.05$) and

the alternative hypothesis that the response rate is $\geq 20\%$ ($P \geq 0.20$). These values were chosen for both arms based on what is clinically relevant per the investigators' experiences. There is no available data at this time for CD30-negative/unknown patients as brentuximab vedotin has not been tested for such patients. Under this design, the probability of early termination under the null hypothesis is 0.599. This design yields a type I error rate, α (probability of concluding that the drug is not effective when it is actually effective) of 0.047 and a power of 0.801 (type II error rate 0.199) when the true response rate is $\geq 20\%$. In the first stage in each cohort, 10 patients will be enrolled. If there are no objective responses, then that cohort will terminate. If ≥ 1 response is observed, then an additional 19 patients will be enrolled in the second stage for a total sample size of 29 patients per cohort. If 3 or fewer responses are observed out of the 29 patients, then Brentuximab will be declared as not worthy of further study for that cohort. If ≥ 4 objective responses are achieved, then brentuximab vedotin will be deemed active in refractory/relapsed NSGCT and worthy of further study.

We estimate enrolling 2 patients/month for the CD30 negative cohort and 1 patient/month for the CD30 positive patients.

12.4 Analysis Datasets

Population	Definition
Enrolled	This will comprise all subjects who meet the eligibility criteria and are registered onto the study.
Efficacy	The efficacy population comprises all patients who have received at least one dose of the study medication. This population will be used for efficacy analysis.
Safety	The safety population comprises all patients who have received at least one dose of the study medication. This set will be used for safety analysis.

12.5 Assessment of Safety

Toxicities will be assessed based on the Common Terminology Criteria for Adverse Events (CTCAE) version 4.0. The maximum grade of each toxicity will be recorded for each patient over the course of treatment (all cycles). Toxicities will be recorded up until 30 days after the last day of treatment. The incidence of treatment delays, dose reductions, and early discontinuations of treatment due to toxicity or patient choice, will also be recorded as a means of assessing the tolerability of treatment for each cohort.

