6.1 Dose Delays and Dose Modifications

Inpatient dose reduction will be allowed depending on the type and severity of toxicity. [Table 1](#) describes the recommended dose modifications for study treatment-associated

toxicity.

The start of the next cycle may be delayed for up to 3 weeks if additional time is required for the patient to recover from study treatment-associated toxicity experienced during the current cycle. Delays of greater than 4 weeks are prohibited without approval of the Sponsor.

Doses reduced for treatment-related toxicity should not be re-escalated without discussion with the Sponsor.

Table 1 Recommended dose modifications for brentuximab vedotin-associated toxicity

Toxicity	Grade 1	Grade 2	Grade 3	Grade 4
Peripheral Neuropathy	Continue at same dose level.	Reduce treatment to 1.2 mg/kg	Withhold until toxicity resolves to \leq Grade 2 or has returned to baseline; resume treatment at 1.2 mg/kg	Discontinue treatment
Nonhematologic	Continue at same dose level.	Continue at same dose level, except in the event of Grade 2 neuropathy.	Withhold dose until toxicity is \leq Grade 2 or has returned to baseline, then resume treatment at the same dose level. ^a	Withhold dose until toxicity is \leq Grade 2 or has returned to baseline, then reduce dose to 1.2 mg/kg and resume treatment, or discontinue at the discretion of the Investigator
Hematologic	Continue at same dose level.	Continue at same dose level.	Withhold dose until toxicity is \leq Grade 2, or has returned to baseline, then resume treatment at the same dose level. ^b Consider growth factor support (G-CSF or GM-CSF) for treatment of neutropenia and prophylaxis in subsequent cycles. If Grade 4 neutropenia recurs despite growth factor support, consider discontinuation or dose	

Toxicity	Grade 1	Grade 2	Grade 3	Grade 4
			reduction to 1.2 mg/kg.	

a. Patients who develop Grade 3 or 4 electrolyte laboratory abnormalities may continue study treatment without interruption.

b. Patients who develop Grade 3 or 4 lymphopenia may continue study treatment without interruption.

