7. STUDY CALENDAR & EVALUATIONS

Procedure	Screening ¹ (≤ 28 days before 1 st dose)	Every Cycle (21 days ± 3 days)	Before cycle 3 & cycle 5	Before cycle 9 & then after every 4 cycles	Post Treatment Safety Assessments ⁶	Follow-Up ¹⁰
Informed consent and medical history	X					
Patient Registration	X					
Brentuximab vedotin administration ²		X				
ECOG Performance Status	X	X			X	
Physical exam ³ , vital signs	X	X			X	
Serum AFP and beta-hCG	X	X			X	X ¹²
CBC (differential & platelets)	X	X ^{4,11}			X	
Complete metabolic panel	X	X ⁴			X	
Magnesium and phosphorus	X	X ⁴			X	
Pregnancy test ⁵	X	X			X	
Concomitant medications	X	X			X	
Adverse event monitoring ⁷		X			X	
Radiologic evaluations ⁸	X		X	X		X ¹²
Archival tissue ⁹	X					
Survival						X

Footnotes:

- 1 All procedures are to be performed ≤ 28 days prior to study drug administration. Screening assessments may be used in place of the Cycle 1 Day 1 assessments if performed within 7 days prior to the Day 1 visit. Standard of care procedures may be used for screening requirements if performed within 28 days prior to study drug administration.
- 2 Brentuximab vedotin is administered on Day 1 of each Cycle. First dose must be administered within 7 days of registration.
- 3 Complete physical exam to be performed within 28 days of first study drug administration (for screening requirements), Day 1 Cycle 1 and at Final Safety Follow-up. At other time-points, a brief symptom-directed exam and ECOG performance evaluation are sufficient. At Screening, height is recorded and body surface area (BSA) calculated
- 4 Hematologic and chemistry parameters (including serum creatinine, AST, ALT, BUN, phosphate, bilirubin, calcium & magnesium) to be performed on Day -3 to Day 1 of every cycle.
- 5 Females of childbearing potential only. Pregnancy tests must be serum at screening and the post treatment safety assessment visit. Urine pregnancy tests are required on Day 1 of each Cycle. A positive urine pregnancy test must be confirmed by a serum pregnancy test and a pelvic US since some NSGCT can secrete beta-hCG. A pelvic US does not need to be repeated with each cycle unless the treating physician thinks it is necessary to do so.
- 6 The post-treatment safety assessment will be done 21 ± 7 days after the last dose of study drug.

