- 7 All SAEs should be collected from C1D1 until the post-treatment safety assessment. SAEs related or possibly related to study treatment or a study procedure should be reported until the patient is off study. Any death occurring within 30 days after study treatment discontinuation must be reported as an SAE regardless of attribution.
- 8 Appropriate radiographic diagnostic procedures (CT scan of chest, abdomen & pelvis) for evaluation of measurable disease at baseline within 28 days of initiation of the study. CT scans and Chest X-ray will be performed as clinically indicated to follow disease per RECIST 1.1. A confirmation CT scan of response will be performed per RECIST as outlined in the protocol. Patients will be followed for progression every 2 months ± 2 weeks for first year from registration. NOTE: existing scans that are no older than 30 days may be used for the screening scan. RECIST 1.1 Guidelines will be used to evaluate response (see Section 9.0).
- 9 Previous surgical specimens or biopsy samples will be collected for CD30 staining. If none is available, the patient will be offered a repeat biopsy to determine CD30 status.
- 10 Follow up for disease progression and survival will be every 2 months ± 2 weeks for first year from registration. Patients who have progressed will be followed for resolution of all study related toxicity.
- 11 CBC should be done between Day 8 and Day 15 of Cycle 1. This lab can be done locally with results faxed to the study team. Detailed instructions and orders will be provided to patients.
- 12 This will be documented for all patients whenever possible as some patients will not have this information available.

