11.1.6 Determining Attribution to the Investigational Agent(s)

Attribution: An assessment of the relationship between the AE and the medical intervention. CTCAE does not define an AE as necessarily "*caused by a therapeutic intervention*". After naming and grading the event, the clinical investigator must assign an attribution to the AE using the following attribution categories:

Relationship	Attribution	Description
Unrelated to investigational agent/intervention	Unrelated	The AE is clearly NOT related
	Unlikely	The AE is doubtfully related
Related to investigational agent/intervention	Possible	The AE may be related
	Probable	The AE is likely related
	Definite	The AE is clearly related

11.2 Adverse Event (AE) Reporting Requirements:

Adverse events (AEs) will be recorded from the time of first study drug administration and for at least 30 days after treatment discontinuation, regardless of whether or not the event(s) are considered related to trial medications. AEs occurring after the post-treatment safety assessment visit can be collected by telephone or other means of communication. All AEs considered related to trial

medication will be followed until resolution, return to baseline, or deemed clinically insignificant, even if this occurs post-trial.

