11.2.1 Participating Site Reporting Responsibilities

11.2.1.1 Reporting to the IU Simon Cancer Center

Any serious adverse event or unanticipated problem occurring within 30 days of the last dose of study drug must be reported to the IU Simon Cancer Center within **1 business day** of notification or discovery of the incident, using the MedWatch Form 3500A (Mandatory Reporting). SAEs that occur greater than 30 days from last dose of study drug must be reported to the IU Simon Cancer Center if the event is possibly, probably, or definitely related to the study drug. This form must be accompanied by a cover letter which: identifies the event, is signed by the local principal investigator or treating physician, includes the applicable study number and title, and contains the following:

- Site assessment of the event attribution to investigational product or study procedure
- Site assessment of event expectedness (expected vs. unexpected)
- Assessment of whether or not the research places subjects at a greater risk of harm than was previously known or recognized
- Assessment of the event's affect on the risk to benefit ratio
- Statement as to whether the informed consent statement should reflect changes in the potential risks involved
- Statement as to whether the event has been reported previously, and if so, whether the frequency is considered unusually high

Send to: IUSCC Clinical Trials Office
 ATTN: Multicenter coordinator/ IUSCC-0568
 [contact]
 E-mail: [contact]

The Multicenter Network Associate Administrator, or designee, will distribute the reports to all participating sites, the FDA and to Seattle Genetics as per section 11.2.2 below. Copies of all serious adverse event reports or unanticipated problems reports will be kept on file in the IU Simon Cancer Center Clinical Trials Office.

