12.7.2 Analysis Plans for Secondary Objectives

- Both PFS and OS will be estimates using the methods of Kaplan and Meier for each cohort separately.
- Toxicities will be summarized by cohort using frequencies and rates calculated as the proportion of patients in the safety population experiencing SAEs, and treatment delays, reductions, and discontinuations due to AEs, and SAEs. Two sets of tables will be generated: one for the overall toxicities and one for toxicities related to the study medication (possibly related, probably related and definitely related). Toxicities will be grouped by system using MedRA preferred terminology. Grade 1 to 4 will be reported individually and also as grade 3/4. Deaths will be reported individually.

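### Calendar footnote 7 stops collecting unrelated non-fatal SAEs at the day 14 to 28 visit, out of line with the protocol's 30-day safety rule (minor)

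*Combined protocol and SAP*

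**What the plan says.** Four places set a 30-day safety window.

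- Section 12.5, and the synopsis in the same words: "Toxicities will be recorded up until 30 days after the last day of treatment".
- Section 11.2: "Adverse events (AEs) will be recorded from the time of first study drug administration and for at least 30 days after treatment discontinuation", whether or not the event is considered related. It adds that events after the post-treatment visit may be gathered by telephone.
- Section 11.2.1.1: "Any serious adverse event or unanticipated problem occurring within 30 days of the last dose of study drug must be reported" to the coordinating center, with no condition on attribution. After day 30 only possibly, probably or definitely related SAEs must be reported.

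The study calendar in Section 7 differs. Footnote 7 reads: "All SAEs should be collected from C1D1 until the post-treatment safety assessment". It then keeps related or possibly related SAEs until the patient is off study, and any death within 30 days of discontinuation. Footnote 6 fixes the visit: "The post-treatment safety assessment will be done 21 ± 7 days after the last dose of study drug". Section 7.3 gives the same timing.

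On the analysis side, Section 12.7.2 reports the proportion of the safety population with SAEs by cohort. It plans two sets of tables, "one for the overall toxicities and one for toxicities related to the study medication".

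**The concern.** The calendar is a natural working reference for site staff, and footnote 7 hangs on its adverse event monitoring row. That row is marked for every cycle and for the post-treatment visit, but not for follow-up. No day 30 contact is scheduled, and the next follow-up contacts come about every two months. No sentence says which rule governs if the footnote and Section 11 disagree.

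The events at risk are a narrow class: SAEs that are non-fatal, judged unrelated, and occur between the visit and day 30. The attribution table in Section 11.1.6 places unlikely in the unrelated group, so SAEs thought doubtfully related belong to this class too. The result is also odd. Under 11.2 a non-serious unrelated event in that interval is recorded, while under the footnote a serious one need not be.

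Safety and tolerability is a secondary objective, and this is an open-label, single-arm, multicenter study. The overall toxicity table is the reader's check on investigators' attribution. If late capture depends on attribution, and sites differ in which rule they follow, that check is a little weaker.

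**Working it through.** **Length of the gap.** Inputs are the visit window (footnote 6) and the 30-day limit (11.2.1.1 and 12.5).

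- Earliest visit: 21 − 7 = day 14. Gap: 30 − 14 = 16 days, and 16/30 = 53% of the window.
- Nominal visit: day 21. Gap: 30 − 21 = 9 days, and 9/30 = 30%.
- Latest visit: 21 + 7 = day 28. Gap: 30 − 28 = 2 days, and 2/30 = 7%.

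**What each rule keeps between the visit and day 30.**

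| Event in the gap | Footnote 7 | 11.2 / 11.2.1.1 |
|---|---|---|
| Related or possibly related SAE | kept | kept |
| Death | kept | kept |
| Non-fatal SAE judged unrelated or unlikely | not kept | kept |

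Only the last row differs.

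**Possible size.** The documents give no SAE rate, so a range is assumed: a proportion q = 5%, 10% or 20% of patients have a non-fatal unrelated SAE per 30 days, at constant hazard. The daily hazard is h = −ln(1 − q)/30, and the share with such an event in a gap of g days is 1 − exp(−h·g). A full cohort is 29 patients (Section 12.3).

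| q | g = 2 | g = 9 | g = 16 |
|---|---|---|---|
| 5% | 0.3% (0.1 of 29) | 1.5% (0.4) | 2.7% (0.8) |
| 10% | 0.7% (0.2) | 3.1% (0.9) | 5.5% (1.6) |
| 20% | 1.5% (0.4) | 6.5% (1.9) | 11.2% (3.3) |

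These figures assume that every site follows footnote 7. They are upper bounds on the change in the any-SAE proportion, because a patient with an earlier, related or fatal SAE is counted already.

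**Allowing for earlier unrelated SAEs.** Suppose instead that 30% of patients have a non-fatal unrelated SAE between the first dose and day 30 after the last, at constant hazard, with a day 21 visit.

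- Two doses: 21 + 30 = 51 days, of which 51 − 9 = 42 are observed. Proportion captured: 1 − 0.70^(42/51) = 25.5%. Missed: 4.5 points, about 1.3 of 29.
- Four doses: 63 + 30 = 93 days, of which 84 are observed. Proportion captured: 1 − 0.70^(84/93) = 27.5%. Missed: 2.5 points, about 0.7 of 29.

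The loss shrinks as treatment lengthens.

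**The case against.** The best reply is that the protocol already answers the question. Four places give 30 days. Section 11.2.1.1 is the dedicated reporting section and uses must, where the footnote uses should. Section 11.2 foresees that the visit can precede day 30 and provides for telephone collection. The footnote does not forbid later collection, so a site that follows Section 11 also satisfies the footnote. On that view this is one stray footnote, and events are lost only if a site lets it override a mandatory rule. Most of this stands, and it is why the point is minor. It does not remove the mismatch: the footnote separates related from unrelated SAEs after the visit, which reads as a deliberate cut-off, and 11.2 only permits the telephone contact without scheduling it.

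A reader might infer more than the documents support:

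- *That all SAE collection ends at the visit, or that a planned 30-day SAE rate rests on contradictory rules.* Footnote 7 continues related SAEs and deaths, and Section 12.7.2 names no 30-day SAE rate.
- *That the windows start from different dates, so that some end as late as day 51 or 72.* This needs treatment discontinuation in 11.2 to mean a later decision date: 21 + 30 = 51 if the decision comes when the next dose is due, or 21 + 21 + 30 = 72 after the hold in Section 6.1, "The start of the next cycle may be delayed for up to 3 weeks". The protocol does not define it so, and 11.2 sets a minimum. Each dose is a single Day 1 infusion (Section 5.2.1), so the last day of treatment and the last dose are naturally the same day.
- *That Section 12.5 takes the maximum grade only over treatment cycles, leaving out the following 30 days.* The next sentence of 12.5 states the 30-day recording period, and the two can be read together.

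**Conclusion.** The mismatch is real and minor. Footnote 7 is the outlier against a 30-day rule stated in the synopsis and in Sections 11.2, 11.2.1.1 and 12.5. Its possible effect is confined to non-fatal SAEs judged unrelated in the last 2 to 16 days of the window, and so to a slight understatement of the overall SAE proportion.

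The length of the gap follows from the documents alone. The patient counts do not: they rest on assumed event rates, constant hazard and every site following the footnote. If every site follows 11.2.1.1 the loss is zero. The related-toxicity table, the primary endpoint and the stage 1 stopping rule do not depend on these events.

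**What to change.** Reword the first sentence of footnote 7 so that every SAE is collected from Cycle 1 Day 1 through 30 days after the last dose, and add a telephone check at day 30 when the post-treatment visit falls earlier. Section 11.2 already allows collection by telephone. The rest of the footnote can stay, and the synopsis and Sections 11.2, 11.2.1.1 and 12.5 need no change for this purpose.

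The cost is a short edit and at most one telephone contact per patient: between 20 contacts (2 × 10, if both cohorts stop at stage 1) and 58 (2 × 29, if both complete). No visit, sample or endpoint is added. The edit is best made before patients leave treatment, because SAEs that were never collected are hard to recover reliably at analysis.
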